7 INVESTIGATIONAL MEDICINAL PRODUCT

7.1 DESCRIPTION OF INVESTIGATIONAL MEDICINAL PRODUCT

Duvelisib drug substance is a white to off-white crystalline powder. The duvelisib drug product is formulated with excipients (Diluent/glidant, disintegrant, and lubricant) that are listed in Food and Drug Administration's (FDA) Inactive Ingredients Database for approved drug products and/or Generally Regarded as Safe (GRAS) in two different capsule strengths (5 mg and 25 mg) for oral delivery.

7.2 DOSAGE AND ADMINISTRATION

7.2.1 Dosage

7.2.1.1 *Duvelisib*

Duvelisib will be administered daily in 28-day cycles (with the exception of Cycle 1 which is 21 days). Duvelisib is administered orally as a capsule formulation and will be supplied by the Sponsor. Duvelisib will be administered as a fixed dose in mg/day and should be administered using the minimal number of capsules necessary.

For an individual subject, dose reductions and discontinuations may be based on the clinical judgment of the Investigator with notification to the Medical Monitor/Sponsor (see [Section 4.2.1](#)).

7.2.1.2 *Ofatumumab*

Subjects assigned to ofatumumab will receive treatment consistent with the approved product labeling: 8 weekly IV doses, starting with an initial IV dose of 300 mg of ofatumumab on Day 1 followed by seven weekly doses of 2000 mg. Thereafter, subjects will receive 2000 mg of ofatumumab once every month for four months through Cycle 7 or until disease progression or unacceptable toxicity (whichever comes first), as outlined in the schedule of assessments. Administration of ofatumumab will not exceed the 12 doses (within 7 cycles) as described in the prescribing information. For an individual subject, dose reductions and discontinuations may be based on the clinical judgment of the Investigator with notification to the Medical Monitor/Sponsor.

7.2.2 Administration

7.2.2.1 *Duvelisib*

Duvelisib will be taken daily BID (every 12±2 hours) in 28-day cycles, except Cycle 1 which is 21 days. An attempt should be made to enable each dose to be taken at approximately the same time of day. Missed doses outside the windows defined above or vomited doses should not be taken or repeated.

Duvelisib doses will be dispensed to the subject so that the subject has enough duvelisib doses until at least the next dispensation visit, taking into account the dispensation visit window.

Duvelisib capsules should be swallowed whole with a glass of water (approximately 8 ounces or 240 mL) at approximately the same time(s) each day. Subjects must avoid grapefruit and grapefruit juice

Duvelisib may be administered without regard to meals.

7.2.2.2 Ofatumumab

Ofatumumab will administered via infusion, as described in the ofatumumab (ARZERRA®) package insert.^{1,2} Please reference country-specific package insert for more details.

7.3 PACKAGING AND LABELING

Duvelisib will be supplied to the clinical trial site as open-label medication. Please refer to the IPI-145-12 Pharmacy Manual for details regarding packaging and labeling of Investigational Product.

7.4 STORAGE AND HANDLING

7.4.1 Duvelisib

Duvelisib must be stored at room temperature (15 to 30°C).

Caution is required when handling duvelisib. Pharmacists should follow standard procedures for the handling of investigational drugs, including avoidance of eye or skin contact with the drug product. If there is exposure to the drug product, provide treatment as necessary for physical exposure (skin washing) or inhalation (move to fresh air) and seek medical advice as necessary.

When duvelisib capsules are distributed for self-administration, they should only be handled by the study subject. After handling capsules, the subject should wash their hands thoroughly. If someone who is not enrolled in a clinical trial involving duvelisib swallows a capsule or inhales drug powder from a broken capsule of duvelisib, they should contact the relevant Principal Investigator to determine whether safety monitoring is necessary. Capsules should always be stored in the container provided to the study subject.

7.4.2 Ofatumumab

Ofatumumab (ARZERRA®) is supplied as a sterile, clear to opalescent, colorless, preservative-free liquid concentrate (20 mg/mL) for dilution and intravenous administration provided in single-use glass vials with a latex-free rubber stopper and an aluminum over seal. Each vial contains either 100 mg ofatumumab in 5 mL of solution or 1000 mg ofatumumab in 50 mL of solution.

Store ARZERRA® refrigerated between 2° to 8°C (36° to 46°F). Do not freeze. Vials should be protected from light.

See ARZERRA® package insert for more details.

7.5 INVESTIGATIONAL MEDICINAL PRODUCT ACCOUNTABILITY**7.5.1 Duvelisib**

The Investigator or designee is responsible for taking an inventory of each shipment of duvelisib investigational supplies received, and comparing it with the accompanying drug accountability form.

All unused duvelisib will be retained at the site. After full drug accountability and reconciliation, the Investigator will dispose of the study drug at the clinical trial site according to site procedures, or at the Sponsor's request will return all duvelisib to the Sponsor, or its designee. If any study drug is lost or damaged, the disposition of the study drug should be documented.

Subjects should be instructed to bring all unused duvelisib to each study visit. The study site should count all capsules that the subject returns, and should take account for taken doses, missed doses, doses reduced due to missing or lost capsules, etc., before dispensing new study drug to the subject. Any subject who does not take the prescribed dose should be requested to return the remaining drug to the clinical trial site for accountability.

7.5.2 Ofatumumab

For Sponsor supplied Ofatumumab, the Investigator or designee is responsible for taking an inventory of each shipment received, and comparing it with the accompanying drug order form.

All unused Ofatumumab will be retained at the site. After full drug accountability and reconciliation, the Investigator will dispose of the study drug at the clinical trial site according to site procedures, or at the Sponsor's request will return all ofatumumab to the Sponsor, or its designee. If any study drug is lost or damaged, the disposition of the study drug should be documented.

7.6 TREATMENT ASSIGNMENT AND BLINDING

This is an open-label extension study for subjects who experience progressive disease while participating in Study IPI-145-07. Enrolled subjects will be assigned to receive the opposite treatment to what they were administered in Study IPI-145-07.

7.7 ASSESSMENT OF COMPLIANCE**7.7.1 Duvelisib**

At each applicable visit, doses will be dispensed to the subject so that the subject will have enough doses until the next applicable visit, taking into account the window for that subsequent visit. Compliance for doses taken outside of the clinic will be assessed by a count of the capsules returned to the study trial site by the subject and review with the subject.

7.7.2 Ofatumumab

Ofatumumab will be administered via infusion for up to 12 infusions as described in the package insert by the test article administrator.

7.8 TREATMENT OF OVERDOSE

In the case of overdose, clinic staff should be notified immediately and supportive care is to be given as indicated. Subjects should be informed to contact their doctor immediately if they have taken an overdose and should stop taking duvelisib.

No data is available regarding over-dosage with ofatumumab. Supportive care is to be given as indicated in the event of an ofatumumab over-dosage.

8 ADVERSE EVENTS AND SERIOUS ADVERSE EVENTS

8.1 DEFINITIONS

The definitions of AEs and SAEs are provided below.

8.1.1 Adverse Event

An AE is any untoward medical occurrence associated with the use of a drug or with study participation, regardless of the relationship of the occurrence to study drug or protocol. An AE can be any unfavorable and unintended sign (including an abnormal laboratory finding), symptom or disease temporally associated with the use of the drug, whether or not considered related to the drug. An AE can arise from any use of the drug, and from any route of administration, formulation or dose, including an overdose.

Medical conditions present prior to the initiation of the study, as well as ongoing changes in laboratory values/conditions that are being treated at baseline, will be captured as an AE if the condition worsens.

8.1.2 Adverse Reactions and Suspected Adverse Reactions

All noxious and unintended responses to a medicinal product related to any dose should be considered adverse drug reactions. Suspected adverse reactions are any adverse events for which there is a reasonable possibility that the drug caused the adverse event. Adverse reactions also include medication errors and uses outside of what is foreseen in the protocol, which may include misuse, abuse, and overdose (intentional or unintentional) of the product.

8.1.3 Serious Adverse Event

An adverse event or suspected adverse reaction is considered serious if, in the view of either the Investigator or Sponsor, it results in any of the following outcomes:

- Results in death
- Is immediately life-threatening
- Requires inpatient hospitalization or prolongation of existing hospitalization, unless hospitalization is for:
 - ◆ Elective or pre-planned treatment for a pre-existing condition that is unrelated to the indication under study and has not worsened since signing the ICF (as documented as medical history on the eCRF), or
 - ◆ Scheduled therapy for the target disease of the study, including admissions for transfusion support or convenience
- Results in persistent or significant disability / incapacity
- Results in congenital anomaly / birth defect.

Important medical events that may not result in death, be life-threatening, or require hospitalization, may be considered a serious adverse drug experience when, based upon

appropriate medical judgment, they may jeopardize the subject and may require medical or surgical intervention to prevent one of the outcomes listed in this definition. Examples of such medical events include allergic bronchospasm requiring intensive treatment in an emergency room or at home, blood dyscrasias or convulsions that do not result in inpatient hospitalization, or the development of drug dependency or drug abuse.

8.2 PROCEDURES FOR ELICITING, RECORDING, AND REPORTING ADVERSE EVENTS

8.2.1 Eliciting and Recording Adverse Events

Subjects will be instructed to report all AEs and will be asked a general health status question at each study visit. All AEs occurring in treated subjects will be recorded in the eCRF from the time of the signing of the ICF until 30 days after the last dose of study treatment. An AE will be followed until it is either resolved, has returned to baseline, or is determined to be a stable or chronic condition. All SAEs occurring from the signing of ICF through 30 days post last study drug will be processed as outlined in [Section 8.2.3](#).

At each required visit during the trial, all AEs that have occurred since the previous visit must be reviewed. The Investigator or appropriate designee must determine if the adverse event is serious or non-serious.

8.2.1.1 Relationship to Study Drug

The Investigator is required to provide an assessment of relationship of AEs and SAEs to study drug. A number of factors should be considered in making this assessment including: 1) the temporal relationship of the event to the administration of study drug; 2) whether an alternative etiology has been identified; and/or 3) biological plausibility. The following guidelines should be used by investigators to assess the relationship of an AE to the administration of the study drug.

Relationship assessments that indicate the event is “Not Drug Related”:

- None: The event is related to an etiology other than the study product administration (the alternative etiology must be documented in the study subject’s medical record).
- Remote: The event is unlikely to be related to the study product and likely to be related to factors other than study product.

Relationship assessments that indicate the event is “Drug Related”:

- Possible: There is an association between the event and the administration of study drug, and there is a plausible mechanism for the event to be related to the study product; but there may also be alternative etiology, such as characteristics of the subject’s clinical status or underlying disease.
- Probable: There is an association between the event and the administration of study drug, there is a plausible mechanism for the event to be related to the study product, and the event could not be reasonably explained by known characteristics of the subject’s clinical status or an alternative etiology is not apparent.

- Definite: There is an association between the event and the administration of study drug, there is a plausible mechanism for the event to be related to the study product, and causes other than study drug have been ruled out and/or the event re-appeared on re-exposure to study drug.

8.2.1.2 Adverse event severity

The Grade of the AE will be assessed according to the NCI-CTCAE Version 4.03. Toxicities that are not specified in NCI-CTCAE Version 4.03 will be defined as follows:

- Grade 1: Mild; asymptomatic or mild symptoms; clinical or diagnostic observations only; intervention not indicated.
- Grade 2: Moderate; minimal, local or noninvasive intervention indicated; limiting age-appropriate instrumental activities of daily living (ADL).
- Grade 3: Severe or medically significant but not immediately life-threatening; hospitalization or prolongation of hospitalization indicated; disabling; limiting self-care ADL.
- Grade 4: Life-threatening consequences; urgent intervention indicated.
- Grade 5: Death related to AE.

Note: it is important to distinguish between SAEs and severe AEs. Severity is a measure of intensity, whereas seriousness is classified by the criteria based on the regulatory definitions as described in [Section 8.2.1.2](#) above.

8.2.2 Specific Instructions for Recording Adverse Events on the eCRF

8.2.2.1 Diagnosis versus Signs and Symptoms

If a diagnosis is known at the time of reporting, this should be recorded in the eCRF and/or SAE Report Form, as applicable, rather than the individual signs and symptoms (eg, record only hepatitis rather than elevated transaminases, bilirubin, jaundice). However, if a constellation of signs and/or symptoms cannot be medically characterized as a single diagnosis or syndrome at the time of reporting, each individual event should be recorded as an SAE or AE on the eCRF (and SAE Report Form, if applicable). If a diagnosis is subsequently established, it should be reported as follow-up on the eCRF (and follow up SAE report, as applicable) and should replace the individual signs and/or symptoms as the event term on the eCRF (and SAE Report Form, if applicable), unless the signs/symptoms are clinically significant.

8.2.2.2 Adverse Events Occurring Secondary to Other Events

In general, AEs occurring secondary to other events (eg, clinical sequelae or a cascade of events) should be identified by their primary cause. For example, if severe vomiting is known to result in dehydration, it is sufficient to record only vomiting as the SAE or AE on the eCRF (and SAE Report Form, if applicable). However, medically significant AEs occurring secondary to an initiating event that are separated in time should be recorded as independent events on the eCRF

(and SAE Report Form, if applicable). For example, if severe vomiting leads to acute renal failure, both events should be recorded on the eCRF.

8.2.2.3 Persistent or Recurrent Adverse Events

A persistent AE is one that extends continuously, without resolution, between subject evaluation time points. Such events should only be recorded once on the AE eCRF (and SAE Report Form, if applicable). If a persistent AE changes in grade, it should be recorded as a new AE on the eCRF.

A recurrent AE is one that occurs and resolves between subject evaluation time points, and subsequently recurs. All recurrent AEs should be recorded on the eCRF (and SAE Report Form if applicable).

8.2.2.4 Abnormal Laboratory Values

If an abnormal laboratory value or vital sign is associated with clinical signs and/or symptoms, the sign or symptom should be reported as an AE or SAE, and the associated laboratory value or vital sign should be considered additional information and collected on the relevant eCRF. If the laboratory abnormality is a sign of a disease or syndrome, only the diagnosis needs to be recorded on the eCRF (and SAE Report Form, if applicable). Abnormal laboratory values will be reported as an AE if the laboratory result:

- requires an adjustment in the trial drug(s) or discontinuation of treatment
- require additional testing or surgical intervention
- is associated with accompanying symptoms
- is considered to be an AE by the Investigator

8.2.2.5 New Cancers

The development of a new primary cancer should be regarded as an AE and will generally meet at least one of the serious criteria (see [Section 8.1](#)). New primary cancers are those that are not the primary reason for the administration of the trial treatment and have developed after the inclusion of the subject into the trial. They do not include metastases of the original cancer.

Progression of the disease under study (disease progression) is not an AE/SAE, unless fatal.

8.2.2.6 Medication Errors, Misuse and Abuse of Study Drug

Overdose, medication error, misuse and abuse are defined as follows:

- *Overdose*: refers to the administration of a quantity of study drug given per administration or cumulative, which is above the maximum dose according to the protocol. Clinical judgment should always be applied.
- *Medication error*: refers to an unintentional error in dispensing or administration of the study drug not in accordance with the protocol.
- *Off-label use*: relates to situations where the study drug is intentionally used for medical purpose not in accordance with the protocol.

- *Misuse*: refers to situations where the study drug is intentionally and inappropriately used not in accordance with the protocol.
- *Abuse*: corresponds to the persistent or sporadic, intentional excessive use of the study drug, which is accompanied by harmful physical or psychological effects.
- *Occupational exposure*: refers to the exposure to the study drug as a result of one's professional or non-professional occupation.

Overdoses, medication errors, abuse or misuse will be collected as part of investigational medicinal product dosing information and/or as a protocol violation, as required. Any AE associated with an overdose, medication error, misuse or abuse of study drug should be recorded on the AE eCRF with the diagnosis of the AE.

8.2.3 Reporting of Serious Adverse Events

8.2.3.1 Immediate Reporting of Serious Adverse Events by Investigator to Sponsor

All SAEs will be reported to the Sponsor or designee within 24 hours of the Investigator's first knowledge of the event, even if the experience does not appear to be related to duvelisib or ofatumumab, from the time of signing ICF through 30 days after the last dose of study drug.

Serious adverse events should be communicated on an SAE Report Form as follows:

- Email: [REDACTED]
- Hotline (Phone): [REDACTED] (USA)
- Fax: [REDACTED] (USA)
- For international numbers, please refer to the SAE Report Form and supporting documentation.

The initial SAE report must be as complete as possible, including details of the current illness and (serious) AE, and an assessment of the causal relationship between the event and the investigational product(s). Information not available at the time of the initial report (eg, final diagnosis, an end date for the AE, or relevant laboratory values received after the report) must be documented on a follow-up SAE Report Form. All SAE follow-up information must be reported in the same timelines as initial information (ie, within 24 hours of the Investigator's first knowledge of information).

At any time after completion of the AE reporting period (ie, 30 days post-treatment), if an Investigator becomes aware of an SAE that is suspected by the Investigator to be related to study drug, the event must be reported as described above.

8.2.3.2 Immediate Reporting of Medical Events of Interest

Reports or laboratory results of AST or ALT >3x ULN in combination with total bilirubin >2 x ULN are medical events of interest, and therefore immediately reportable events, even if the events do not meet serious adverse event criteria.

Clinical findings of Grade 3 or higher rash are medical events of interest, and therefore immediately reportable events, even if the events do not meet serious adverse event criteria.

Pre-existing skin conditions that recur would not meet this definition unless the recurrence is of a greater severity/frequency than previously experienced.

All medical events of interest will be reported to the Sponsor or designee within 24 hours of the Investigator's first knowledge of the event, even if the experience does not appear to be related to study drug. Medical Events of Interest should be communicated on the SAE / MEOI report form, as described above for SAEs.

Any occupational exposure or exposure of an individual not enrolled in the study to the investigational medicinal product must be reported to the Sponsor or designee within 24 hours of the Investigator's first knowledge of the event, even if the exposure does not result in an adverse event. Unintentional exposures should be communicated on the SAE/MEOI report form, as described above for SAEs.

8.2.3.3 Reporting of Serious Adverse Events to the Institutional Review Board (IRBs)/ Ethics Committee

Verastem or designee shall notify the Investigator and/or the IRBs/ECs per institutional guidelines of potential serious risks from clinical trials or any other sources, including the following:

- Suspected adverse reaction that is both serious and unexpected.
- Any findings from other studies that suggest a significant risk in humans exposed to the drug.
- Any finding from animal or *in vitro* testing that suggest a significant risk to humans exposed to the drug, such as mutagenicity, teratogenicity, or carcinogenicity; or report of significant organ toxicity at or near the expected human exposure.

Verastem or designee shall notify Central Ethics Committees (CEC) of new serious, related, and unexpected AE(s) or significant risks to subjects, per country requirements.

The Investigator will notify Local Ethics Committees (LECs) of serious, related and unexpected AE(s) or significant risks to subjects, per local country requirements.

The Investigator must keep copies of all AE information, including correspondence with Verastem and the IRB/EC on file.

8.2.3.4 Reporting of Serious Adverse Events to Regulatory Authorities

Verastem or designee shall notify Regulatory Authorities of serious, unexpected adverse reactions or other adverse events, per local requirements. Expectedness will be determined using the current duvelisib Investigator Brochure and ofatumumab United States Package Insert (USPI; 2009) or the Summary of Product Characteristics (SmPC).

8.2.4 Pregnancy and In Utero Drug Exposure

Since duvelisib has not been evaluated in pregnant or nursing women, the treatment of pregnant women or women of childbearing potential who are not using effective contraception is contraindicated (see [Section 5.2.1](#) and [Section 6.2.1](#) for instructions on pregnancy testing and birth control).

Pregnancies occurring in subjects or partners of male subjects during the study treatment period until 30 days after the subject's last dose of study treatment are considered immediately reportable events. If a pregnancy occurs in a subject, study treatment must be discontinued immediately. The pregnant woman should be referred to an obstetrician/gynecologist experienced in reproductive toxicity for further evaluation and counseling.

The pregnancy must be reported to Verastem or designee within 24 hours of the Investigator's knowledge of the pregnancy using the Pregnancy Notification Form as follows:

- Hotline (Phone): [REDACTED] (USA)
- Fax: [REDACTED] (USA)
- For International numbers, please refer to the Pregnancy Notification Form and supporting documentation.

The Investigator will follow the pregnant woman until completion of the pregnancy, and must notify Verastem of the outcome within 24 hours of the Investigator's knowledge of the pregnancy outcome. The Investigator will provide this information on the Pregnancy Outcome Report Form. This notification includes pregnancies resulting in live, "normal" births.

If the pregnant subject experiences an SAE during pregnancy, or the outcome of the pregnancy meets the criteria for immediate classification as an SAE (ie, spontaneous abortion [any congenital anomaly detected in an aborted fetus is to be documented], stillbirth, neonatal death, or congenital anomaly), the Investigator should follow the procedures for reporting SAEs (ie, report the event to Verastem within 24 hours of the Investigator's knowledge of the event).

All neonatal deaths and congenital anomalies that occur within 30 days of birth (regardless of causality) should be reported as SAEs to Verastem. In addition, any infant death or congenital anomaly occurring after 30 days that the Investigator suspects is related to the in utero exposure to the study drug should also be reported to Verastem.

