	Subjects assigned to ofatumumab will receive treatment consistent with the approved product labeling: 8 weekly infusions, starting with an initial dose of 300 mg ofatumumab IV on Day 1 followed by 7 weekly doses of 2000 mg. Thereafter, subjects will receive 2000 mg ofatumumab once every month for four months or until disease progression or unacceptable toxicity (whichever comes first), as outlined in the schedule of assessments. Administration of ofatumumab will not exceed the 12 doses (within 7 cycles) as described in the prescribing information.	
Study Population:	All subjects previously enrolled in Study IPI-145-07 (approximately 300 subjects) who experience radiologically-confirmed disease progression while participating in that study may be eligible for this study; it is anticipated that approximately 150 subjects may enroll.	
Study Duration:	Following treatment with duvelisib, study subjects will be followed until disease progression, discontinuation from study participation, or start of subsequent therapy, whichever comes first. Following treatment with ofatumumab, study subjects will be followed until disease progression, discontinuation from study participation, start of subsequent therapy, or 2 years (24 cycles) from their first dose, whichever comes first.	
Study Centers:	All study sites initiated for Study IPI-145-07 will be eligible to participate in this extension study; for Study IPI-145-07 enrollment is anticipated at 74 sites, with 15 sites in the US and 59 sites outside the US.	
Inclusion Criteria:	Subjects are eligible for inclusion in this extension study if they meet the following criteria: 1. Received either duvelisib or ofatumumab while participating in Study IPI-145-07 and experienced radiologically-confirmed disease progression	

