5.2 ENTRY CRITERIA

5.2.1 Inclusion Criteria

Subjects are eligible for inclusion in the extension study if they meet the following criteria:

1. Received either duvelisib or ofatumumab while participating in Study IPI-145-07 and experienced radiologically-confirmed disease progression
2. Diagnosis of active CLL or SLL that meets at least one of the IWCLL 2008 criteria for requiring treatment (Binet Stage \geq B and/or Rai Stage \geq I)
3. Measurable disease with a lymph node or tumor mass >1.5 cm in at least one dimension as assessed by computed tomography (CT)
4. Eastern Cooperative Oncology Group (ECOG) performance status of 0 to 2 (corresponds to Karnofsky Performance Status [KPS] $\geq 60\%$)
5. Must meet the following laboratory parameters:
 - a) Serum aspartate transaminase (AST/SGOT) or alanine transaminase (ALT/SGPT) ≤ 3 x upper limit of normal (ULN)
 - b) Total bilirubin ≤ 1.5 x ULN
 - c) Serum creatinine ≤ 2.0 x ULN
 - d) Hemoglobin ≥ 8.0 g/dL with or without transfusion support
 - e) Platelet count $\geq 10,000$ μ L with or without transfusion support
6. For women of childbearing potential (WCBP): negative serum β -human chorionic gonadotropin (β hCG) pregnancy test within 1 week before first dose (WCBP defined as a sexually mature woman who has not undergone surgical sterilization or who has not been naturally post-menopausal for at least 24 consecutive months [women ≤ 55 years] or 12 consecutive months [women >55 years])
7. Willingness of male and female subjects who are not surgically sterile or postmenopausal to use medically acceptable methods of birth control from the first dose of study drug to 30 days after the last dose of duvelisib and for 12 months after last dose of ofatumumab. Sexually active men, and women using oral contraceptive pills, should also use barrier contraception

8. Ability to voluntarily sign consent for and adhere to the entire study visit schedule and all protocol requirements
9. Signed and dated institutional review board (IRB)/independent ethics committee (IEC)-approved informed consent form (ICF) before any study specific screening procedures are performed

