6.5.1.3 Follow-up

For subjects who completed treatment or discontinued treatment with duvelisib or ofatumumab early due to reasons other than disease progression and remain on study, CBC and differential count will be performed approximately 2 months after the last on-treatment Disease Response Assessment, and every 2 months thereafter through 18 cycles and every 3 cycles thereafter or until PD, subject withdrawal, or start of subsequent therapy. All other disease assessments should occur approximately 6 months after the last on-treatment Disease Response Assessment, and every 6 months thereafter until PD, subject withdrawal, or start of subsequent therapy. For subjects in the ofatumumab treatment arm, their final assessment will be at Cycle 24. The following assessments should be performed as outlined in [Table 4](#).

Every 2 months

- CBC and differential count

Every 3 months (from Cycle 18)

- CBC and differential count

Every 6 months

- CT scans of chest, abdomen and pelvis
- Bone marrow biopsy and bone marrow aspiration
- Focused physical examination, ECOG performance status, and disease-related constitutional symptoms

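### Pregnancy notification after ofatumumab stops at 30 days although contraception is required for 12 months

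*Protocol*

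**What the plan says.** **Notification.** Protocol 8.2.4 covers pregnancies in participants and in the partners of male participants. Those arising on treatment or within 30 days of the "last dose of study treatment are considered immediately reportable events". The rule is the same for both drugs. For notified pregnancies it adds: "The Investigator will follow the pregnant woman until completion of the pregnancy, and must notify Verastem of the outcome within 24 hours". Normal births are included in that duty.

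**Contraception.** Inclusion criterion 7 (Protocol 5.2.1, repeated in the synopsis) requires birth control from the first dose until "30 days after the last dose of duvelisib and for 12 months after last dose of ofatumumab".

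**Adverse outcomes.** Three provisions could apply after day 30:
- Protocol 8.2.3.1 has no end date, but applies only "if an Investigator becomes aware of an SAE that is suspected by the Investigator to be related to study drug".
- Protocol 8.2.4 calls for SAE reporting where "the outcome of the pregnancy meets the criteria for immediate classification as an SAE (ie, spontaneous abortion", and goes on to list stillbirth, neonatal death and congenital anomaly. It sets no causality condition or time limit of its own.
- Protocol 8.2.4 also states: "All neonatal deaths and congenital anomalies that occur within 30 days of birth (regardless of causality) should be reported as SAEs". Infant deaths and anomalies after that point are reportable if the investigator suspects in utero exposure as the cause.

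**Follow-up.** Protocol 6.5.1.3 states: "For subjects in the ofatumumab treatment arm, their final assessment will be at Cycle 24". The synopsis (Study Duration) ends ofatumumab follow-up at progression, discontinuation, "start of subsequent therapy, or 2 years (24 cycles) from their first dose, whichever comes first".

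**The concern.** The contraception rule implies that the protocol treats the 12 months after ofatumumab as a period in which conception should be avoided. For most of that period a contraceptive failure known to the investigator need not be notified unless it ends in one of the listed adverse outcomes. Section 8.2.4 itself points to 5.2.1 for birth control, so the two provisions are linked, yet their windows agree for one drug and differ for the other. No section gives a reason for the difference.

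What is at stake is fetal-safety information in one arm. Uneventful pregnancies and normal births could go unrecorded, so an adverse outcome that did reach the sponsor would have no count of exposed pregnancies beside it. The text also leaves unclear whether the SAE provisions of 8.2.4 reach pregnancies conceived after the 30-day window.

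**Working it through.** The plan states no figure for this gap, so there is none to reproduce. The check compares two stated windows and places the result on the visit schedule.

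**Gap = contraception window − notification window, both counted from the last dose**

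| Drug | Contraception (criterion 7) | Notification (8.2.4) | Gap |
|---|---|---|---|
| Duvelisib | 30 days | 30 days | 30 − 30 = 0 days |
| Ofatumumab | 12 months ≈ 365 days | 30 days | 365 − 30 = 335 days |

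335 / 365 = 91.8%. Counting 12 months as 360 to 366 days gives 330 to 336 days.

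**Position on the schedule.** Cycle 1 lasts 21 days and later cycles 28 (Protocol 4.1), so for k ≥ 2, Cycle k Day 1 = day 22 + 28(k − 2).
- Twelfth and last ofatumumab dose, Cycle 7 Day 1: 22 + 28 × 5 = day 162.
- Notification ends: 162 + 30 = day 192.
- Contraception ends: 162 + 365 = day 527.
- Final assessment, Cycle 24 Day 1: 22 + 28 × 22 = day 638, which is later than day 527.

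A subject dosed on schedule and followed to Cycle 24 is therefore in study follow-up for the whole gap. One who leaves at progression by day 192 is in follow-up for none of it. Time under study contact within the gap thus ranges from 0 to 335 days.

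**Scheduled contacts in the gap.** Assume visits fall on the Table 4 cycles, with blood counts every second cycle to Cycle 18 and every third after that. Counts then fall at Cycles 10, 12, 14, 16 and 18 (days 246, 302, 358, 414 and 470), which makes 5 contacts. Two of these, Cycles 12 and 18, include full disease assessments. Cycle 8 (day 190) falls just before the gap and Cycle 21 (day 554) after it. Protocol 6.5.1.3 times follow-up from the last on-treatment assessment, so actual dates may differ. The 335 days do not depend on this.

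**Do other provisions fill the gap?** None extends notification of the pregnancy itself. AE and SAE collection also ends 30 days after dosing (Protocol 6.3.4 and 8.2.1). The three adverse-outcome provisions, even read broadly, do not cover uneventful pregnancies and normal births. A pregnancy that began by day 30 but was detected later can be read as already covered, so the gap concerns those beginning after day 30.

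**The case against.** The strongest reply is that the two windows serve different purposes. Contraception is a precaution asked of subjects, while notification is a duty on investigators. The 30-day limit matches the protocol's other safety windows, and nothing in the protocol requires notification to run as long as contraception. That stands: the text is not self-contradictory. It does not explain why the duty stops for ofatumumab while the precaution continues. Section 8.2.4 gives only duvelisib in its rationale, so a duvelisib window may have been applied to both arms, but that is inference.

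Second, the serious outcomes are largely handled. This stands in part. Read without an implied time limit, the 8.2.4 provisions would catch losses, neonatal deaths and anomalies. The text does not say so for later conceptions, and ordinary pregnancies remain outside.

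Third, no consequence has been shown. SAP section 8 gives 8 subjects in this arm, which is too few for a usable pregnancy denominator. This stands and limits the importance of the point, although 8 need not be the final count because Protocol 10.10 keeps enrolment open while the parent study runs.

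Fourth, the remedy reaches only some subjects. They leave at progression, no data may be sought after consent is withdrawn (Protocol 4.4), and pregnancy tests stop with treatment (Protocol 6.3.2). This also stands: the count would stay incomplete.

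**Conclusion.** The mismatch holds. After ofatumumab, about 335 of 365 nominal days of required contraception carry no stated duty to notify a pregnancy as such or follow it to outcome; for duvelisib the gap is zero. Adverse outcomes in that period are partly covered.

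This is a minor design point, worth correcting because correction is cheap. It does not affect ORR, DOR or PFS, or any planned analysis. The 335 days rest on reading 12 months as about 365 days, and the schedule positions on dosing without delay. No number of missed pregnancies can be estimated, because the documents do not give the number of women of childbearing potential or of men with such partners, and it may be zero.

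**What to change.** Amend Protocol 8.2.4 so that a pregnancy in a participant, or in a male participant's partner, is reportable if it arises by 30 days after the final duvelisib dose or 12 months after the final ofatumumab dose, once the investigator learns of it. Apply the same follow-up to outcome, and state that the section's SAE provisions apply to these pregnancies too. If the sponsor prefers to keep 30 days for ofatumumab, it should say why that suffices.

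The text change is one or two sentences, and the ofatumumab gap falls from about 335 days to 0. No visit, test or data-collection schedule changes. The costs are somewhat longer awareness-based reporting in one small arm and the handling of an amendment: ethics committees must be informed (Protocol 10.4), and any resulting change to the consent form needs approval and possibly re-signature (Protocol 10.2). Bundling it with another amendment would reduce that burden. In practice the duty would operate mainly for subjects still in follow-up.
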